**5.2 Selection of Study Population****5.2.1 Inclusion Criteria**

1. Subjects who have been on ADA monotherapy (40 mg eow or greater) for at least 16 weeks but, who in the opinion of the Investigator, have shown a sub-optimal response to treatment (sub-optimal response defined as subjects with an unsatisfactory response to treatment, based on Investigator assessment) and have a PGA of  $\geq 3$  and a PASI of  $\geq 5$ ; or  
Subjects who after an initial positive response to ADA monotherapy (40 mg eow or greater) have failed to maintain an optimal level of response, based on the opinion of the Investigator (sub-optimal response defined as subjects with an unsatisfactory response to treatment based on Investigator assessment) and have a PGA of  $\geq 3$  and a PASI of  $\geq 5$ ;
2. Subjects who are receiving 40 mg ADA once weekly must be on ADA 40 mg eow for 8 weeks prior to screening;
3. Subjects with at least a 6 month history of chronic plaque Ps;
4. Subjects greater than or equal to 18 years of age;
5. If female, subject is either not of childbearing potential, defined as postmenopausal for at least 1 year or surgically sterile (bilateral tubal ligation, bilateral oophorectomy or hysterectomy) or is of childbearing potential and is practicing one of the following methods of birth control throughout the study and for 150 days after the last dose of study drug:
  - Condoms, sponge, foams, jellies, diaphragm or intrauterine device (IUD);
  - Contraceptives (oral, parenteral, transdermal) for three months prior to study drug administration;
  - A vasectomized partner.

If the male subject is sexually active with female partner(s) of childbearing potential, he must agree, from Study Day 1 through 150 days after the last dose of study drug to practice the protocol specified contraception (Section 5.2.4).

6. The results of the serum pregnancy test performed during the Screening Period and urine pregnancy test performed at the Baseline Visit must be negative for females of childbearing potential;

- 
7. Subject is judged to be in good general health as determined by the Investigator based upon the results of medical history, laboratory profile, physical examination, chest X-ray (CXR), and 12-lead electrocardiogram (ECG) performed during Screening;

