## **5.2.4 Contraception Recommendations and Pregnancy Testing**

For female subjects:

- If female, subject must be either postmenopausal defined as: Age  $> 55$  years with no menses for 12 or more months without an alternative medical cause.
- Age  $\leq 55$  years with no menses for 12 or more months without an alternative medical cause AND an FSH level  $> 40$  IU/L.

OR

- Permanently surgically sterile (bilateral oophorectomy, bilateral salpingectomy or hysterectomy).
- Practicing at least one of the following methods of birth control, on Study Day 1 (or earlier) through at least 150 days after the last dose of study drug.
  - Combined (estrogen and progestogen containing) hormonal contraception (oral, intravaginal, transdermal) associated with the inhibition of ovulation, initiated at least 3 month prior to Study Day 1.
  - Progestogen-only hormonal contraception (oral, injectable, implantable) associated with inhibition of ovulation, initiated at least 3 month prior to Study Day 1.
  - Bilateral tubal occlusion/ligation.
  - Vasectomized partner(s), provided the vasectomized partner has received medical assessment of the surgical success and is the sole sexual partner of the WOCBP trial participant.
  - Intrauterine device (IUD).
  - Intrauterine hormone-releasing system (IUS).
  - True abstinence: Refraining from heterosexual intercourse when this is in line with the preferred and usual lifestyle of the subject (periodic abstinence] e.g., calendar, ovulation, symptothermal, post-ovulation methods] and withdrawal are not acceptable).

For male subjects:

If the male subject has a female partner who is postmenopausal or permanently sterile (bilateral oophorectomy, bilateral salpingectomy or hysterectomy), no contraception is required.

If the male subject is sexually active with female partner(s) of childbearing potential, he must agree from Study Day 1 through 150 days after the last dose of study drug to practice contraception with:

- Condom use and female partner(s) using at least one of the contraceptive measures (as defined in the protocol for female study subjects of childbearing potential).
- True abstinence: Refraining from heterosexual intercourse-when this is in line with the preferred and usual lifestyle of the subject. (Note: Periodic abstinence (e.g., calendar, ovulation, symptothermal, post-ovulation methods] and withdrawal are not acceptable).

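### The female part of inclusion criterion 5 was not aligned with Section 5.2.4: it accepts five barrier methods that 5.2.4 does not list for women

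*Protocol*

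**What the plan says.** Protocol 5.2.1, criterion 5, treats a woman as "not of childbearing potential, defined as postmenopausal for at least 1 year or surgically sterile (bilateral tubal ligation, bilateral oophorectomy or hysterectomy", and otherwise requires one listed birth control method during the study and for 150 days after the last dose. The first bullet of that list is "Condoms, sponge, foams, jellies, diaphragm or intrauterine device (IUD". The other two cover oral, parenteral or transdermal contraceptives used for three months beforehand, and a vasectomized partner. The paragraph on male subjects then refers to Section 5.2.4; the part on women does not.

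Section 5.2.4 is headed "Contraception Recommendations and Pregnancy Testing". Its body says a female subject must be postmenopausal, permanently surgically sterile, or "Practicing at least one of the following methods of birth control, on Study Day 1 (or earlier". Its methods are combined hormonal, progestogen-only hormonal, tubal occlusion or ligation, vasectomized partner, IUD, hormone-releasing intrauterine system (IUS), and true abstinence. Up to age 55, menopause requires "no menses for 12 or more months without an alternative medical cause AND an FSH level" above 40 IU/L. Male subjects with partners of childbearing potential need "Condom use and female partner(s) using at least one of the contraceptive measures (as defined in the protocol for female study subjects", or true abstinence.

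Synopsis criterion 5 asks only that the woman practise birth control and names no method.

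**The concern.** Every subject takes methotrexate, and the protocol's summary of changes gives its embryotoxic and teratogenic effects as the reason for adding pregnancy tests at Weeks 8 and 16. Tests detect a pregnancy after it has begun; the list of accepted methods is what is meant to prevent one. The protocol contains two such lists for women, and they disagree on whether a barrier method alone is enough.

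Section 5.3.1.1 makes the inclusion and exclusion criteria the test for enrolment. A site working from criterion 5 could enrol a woman whose only method is a diaphragm and find every item on its checklist met. A site working from 5.2.4 would not enrol her. With approximately 25 sites, both readings could be in use. It is also unclear whether the first site has a reportable deviation under Section 7.0, because the listed category is failure to satisfy entry criteria and she satisfies criterion 5.

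**Working it through.** No figure in the plan is in question, so the check sets the two texts side by side. It reads the three bullets for women in 5.2.4 (menopause, permanent sterility, listed method) as alternatives, which is the only reading that makes sense.

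**1. Methods in the first bullet of criterion 5, for women**

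| Method | Criterion 5 | Section 5.2.4, women |
|---|---|---|
| Condoms | accepted alone | not listed |
| Sponge | accepted alone | not listed |
| Foams | accepted alone | not listed |
| Jellies | accepted alone | not listed |
| Diaphragm | accepted alone | not listed |
| IUD | accepted | listed |

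Five of six are absent from 5.2.4 and one of six is shared. Condoms do appear in 5.2.4, but only for male subjects and only together with a method used by the partner.

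**2. Other methods in criterion 5.** Hormonal contraception and a vasectomized partner are in both texts. Section 5.2.4 adds conditions: "hormonal contraception (oral, intravaginal, transdermal) associated with the inhibition of ovulation, initiated at least 3 month prior to Study Day 1" for combined methods, a matching condition for progestogen-only methods, and for vasectomy "provided the vasectomized partner has received medical assessment of the surgical success and is the sole sexual partner of the WOCBP trial participant". These are mostly clarifications and are not counted as conflicts.

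**3. Definitions**

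- *Menopause.* Criterion 5 asks for at least 1 year. Section 5.2.4 asks for 12 months without menses and, at age 55 or below, the FSH result as well. A woman of 55 or below who is judged postmenopausal for a year but has no qualifying FSH result needs no contraception under criterion 5. Under 5.2.4 she needs a listed method or surgical sterility. Protocol Table 2 lists no FSH test.
- *Tubal ligation.* Criterion 5 counts it as sterility. Section 5.2.4 counts it as a birth control method and leaves it out of permanent sterility. The woman can enrol under either text, but she is exempt from pregnancy testing under the first and tested under the second.
- *Who is tested.* Criterion 6 and Table 1 footnotes n and o depend on childbearing potential. The exemption in the Pregnancy Tests part of 5.3.1.1 points to definitions given above without saying which. Its reference to permanent surgical sterility matches 5.2.4, so that is the likelier target, but criterion 5 also precedes it.

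**4. The other direction.** Section 5.2.4 accepts bilateral salpingectomy, true abstinence, intravaginal hormonal contraception and the IUS. Criterion 5 lists none of them. Here the error is needless exclusion, not exposure.

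**5. Is there a rule of precedence?** The synopsis, summary of changes, criteria, study procedures, Section 7.0 and SAP contain none. The summary of changes says 5.2.4 was added to make acceptable contraception more precise, which shows intent but does not rank the texts.

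**The case against.** The best case on the other side is that the two texts can be applied together. Section 5.2.4 says must. Criterion 9, itself an inclusion criterion, requires subjects to comply with the protocol, and Section 7.0 makes the Principal Investigator responsible for all protocol requirements. The male paragraph of criterion 5 treats 5.2.4 as the contraception the protocol specifies, so the word Recommendations in its heading carries little weight. A woman with an IUD satisfies both lists; a barrier-only woman fails one of them and should not be enrolled. On this view criterion 5 holds a stale list, not a permission.

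Much of this stands: the stricter list is the better reading. It does not remove the conflict. Criterion 9 is a general clause that says nothing about contraception or about which list prevails, and a reader has to infer the answer.

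Three stronger readings are tempting, and the documents do not support them:

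- A reader might infer that the protocol positively permits barrier-only use, or that such women have been enrolled. The first ignores 5.2.4 and criterion 9; nothing in the documents shows the second.
- A reader might use the number of methotrexate doses between pregnancy tests, or the time after the last test, to measure the risk. Those intervals are the same for every method under either list and would not change with the fix. Pregnancies are in any case collected through 150 days after the last dose (Section 6.1.6).
- A reader might count the hormonal and vasectomy wording as further contradictions. It is mainly added precision.

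**Conclusion.** The female part of criterion 5 is wrong as written and should be fixed. It accepts as sufficient five methods that the protocol's own mandatory list omits, and its definitions of menopause and surgical sterility differ from those in 5.2.4.

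The effect is confined to patient safety and eligibility. No endpoint, analysis population or estimate changes. The number of women affected cannot be derived: about 50 subjects of both sexes are planned, and the documents give neither a sex split nor contraceptive failure rates, so none is assumed. Several safeguards hold whichever list is used: exclusion 10, the negative screening and baseline tests for women of childbearing potential, their tests at Weeks 8, 16 and 24, and withdrawal on pregnancy (Section 5.4.1).

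Confidence is high for the textual mismatch. It is lower for what sites would do, since a careful site would probably follow 5.2.4. The menopause case is narrower still, because it depends on the investigator's judgement.

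**What to change.** Let Section 5.2.4 govern:

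- In criterion 5, replace the female definitions and method list with a sentence requiring female subjects to meet Section 5.2.4, and align synopsis criterion 5.
- In the Pregnancy Tests part of 5.3.1.1, make the exemption refer to Section 5.2.4 by number.
- In the 5.2.4 heading, change Recommendations to Requirements.
- Require barrier-only women already on methotrexate to move to a listed method or be discussed with the Medical Monitor. They cannot meet the hormonal lead time of three months before Study Day 1, so they would need a method without one, such as an IUD or IUS.

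Once criterion 5 holds no list of its own, the male text's pointer to the methods defined for female subjects has only one target. Adding FSH to the screening draw for women of 55 or below with 12 months' amenorrhoea is optional: without a qualifying result, 5.2.4 already requires a listed method or surgical sterility.

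The cost is a wording amendment, which Section 9.1 makes subject to IEC/IRB approval before implementation. A few barrier-only women may have to change method or not enrol, in a study already reduced for slow recruitment. The hormonal lead time exceeds the 35-day screening period, but 5.2.4 states none for the other methods. In return, women with salpingectomy, true abstinence, intravaginal hormonal contraception or an IUS become clearly eligible on this criterion.

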**5.2.2                   Exclusion Criteria**

1. Subject has any contraindications to MTX or ADA;
2. Subject has a previous failed response or poor tolerance to ADA;
3. Subject has a poorly controlled medical condition, such as uncontrolled diabetes, unstable heart disease, congestive heart failure, recent cerebrovascular accidents and any other condition which, in the opinion of the Investigator, would put the subject at risk by participation in the study;
4. Subject has a history of clinically significant hematologic (e.g., severe anemia, leukopenia, thrombocytopenia), renal or liver disease (e.g., fibrosis, cirrhosis, hepatitis);
5. Subject has history of neurologic symptoms suggestive of central nervous system (CNS) demyelinating disease and/or diagnosis of central demyelinating disease;
6. Subject has evidence of dysplasia or history of malignancy (including lymphoma and leukemia) other than a successfully treated non-metastatic cutaneous squamous cell or basal cell carcinoma or localized carcinoma in situ of the cervix;
7. Subject has a history of listeriosis, histoplasmosis, untreated TB, persistent chronic infections, or recent active infections requiring hospitalization or treatment with intravenous (iv) anti-infectives within 30 days or oral anti-infectives within 14 days prior to the Baseline visit;
8. Subject is known to have immune deficiency, history of HIV or is immunocompromised;
9. Subject currently uses or plans to use anti-retroviral therapy at any time during the study;
10. Female subject who is pregnant or breast-feeding or considering becoming pregnant during the study or for 150 days after the last dose of study medications;
11. Subject has a history of clinically significant drug or alcohol usage in the last year (12 months) or cannot maintain an alcohol intake of 30 g a day or less throughout the study. One standard drink is defined as 180 mL/6 oz (approx. 10 g) of wine, 360 mL/12 oz (approx. 15 g) of regular beer, or 45 mL/1.5 oz (approx. 10 g) of spirits;
12. Screening clinical laboratory analyses show any of the following abnormal laboratory results:
  - Aspartate transaminase (AST) or alanine transaminase (ALT) >2x the upper limit of normal (ULN);

- Serum total bilirubin > 1.5 mg/dL (> 26 micromol/L), except for subjects with Gilbert's Syndrome;
  - Creatinine > 1.5 mg/dL (133 micromol/L) in subjects ≤ 65 years old and > ULN range in subjects > 65;
  - Positive Hepatitis B or C serology indicative of previous or current infection.
13. Subject is considered by the Investigator, for any reason, to be an unsuitable candidate for the study;
14. The following treatments are prohibited for all subjects during the study:
- Phototherapy (PUVA (within 4 weeks of the baseline visit) and/or UVB (within 2 weeks of the baseline visit));
  - Other biologic therapies (including any other anti-TNF) within 4 weeks of the baseline visit (except for ADA);
  - Any investigational agents of chemical or biologic nature within a minimum of 30 days or 5 half-lives (whichever is longer) of the drug prior to the Baseline visit;
  - Any other systemic drug therapies for Ps, including cyclosporine, retinoids, and fumaric acid esters, within 4 weeks of the baseline visit;
  - Oral or injectable corticosteroids, new prescription topical therapies (including shampoos with corticosteroids), or changes in the concentration of current prescription of topical therapies (including corticosteroids) that are being used, within 2 weeks of the baseline visit. However, subjects may continue using previously prescribed topical therapies (including corticosteroids) during the study. Inhaled corticosteroids are allowed. .
15. Prior exposure to biologics that have a potential or known association with PML (i.e., natalizumab (Tysabri®) or rituximab (Rituxan®));
16. Subjects with any active viral infection that based on the investigator's clinical assessment makes the subject an unsuitable candidate for the study.
17. Male subject who is considering fathering a child or donating sperm during the study or for approximately 150 days after the last dose of study drug.

These criteria reflect the usual exclusion criteria in Phase III studies assessing ADA and MTX in the treatment of Ps.

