**Main Exclusion (contd.):**

11. Subject has a history of clinically significant drug or alcohol usage in the last year or cannot maintain an alcohol intake of 30 g a day or less throughout the study (one standard drink is defined as 180 mL/6 oz (approx. 10 g) of wine, 360 mL/12 oz (approx. 15 g) of regular beer, or 45 mL/1.5 oz (approx. 10 g) of spirits;
12. Screening clinical laboratory analyses show any of the following abnormal laboratory results:
  - Aspartate transaminase (AST) or alanine transaminase (ALT) > 2x the upper limit of normal (ULN);
  - Serum total bilirubin > 1.5 mg/dL (> 26 micromol/L), except for subjects with Gilbert's Syndrome;
  - Creatinine > 1.5 mg/dL (133 micromol/L) in subjects ≤ 65 years old and > upper limit of normal range in subjects > 65;
  - Positive Hepatitis B or C serology indicative of previous or current infection.
13. Subject is considered by the Investigator, for any reason, to be an unsuitable candidate for the study;
14. The following treatments are prohibited for all subjects during the study:
  1. Phototherapy (PUVA (within 4 weeks of the Baseline Visit) and/or UVB (within 2 weeks of the Baseline Visit);
  2. Other biologic therapies (including any other anti-TNF) within 4 weeks of the Baseline Visit;
  3. Any investigational agents of chemical or biologic nature within a minimum of 30 days or 5 half-lives (whichever is longer) of the drug prior to the Baseline visit ;
  4. Any other systemic drug therapies for Ps within 4 weeks of the Baseline Visit;
  5. Oral or injectable corticosteroids, new prescription topical therapies, or changes in the concentration of current prescription topical therapies (including corticosteroids) that are being used, within 2 weeks of the Baseline Visit. Subjects may continue using previously prescribed topical therapies (including corticosteroids) during the study.
15. Prior exposure to biologics that have a potential or known association with Progressive multifocal leukoencephalopathy PML (i.e., natalizumab (Tysabri®) or rituximab (Rituxan®));
16. Subjects with any active viral infection that based on the investigator's clinical assessment makes the subject an unsuitable candidate for the study;

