### **5.2.3.2 Concomitant Therapy**

Any medication, including vaccines, the subject receives during the study (and within 28 days of the Screening visit) should be recorded. Subjects may continue using previously prescribed topical therapies (including corticosteroids) during the study. However, application of these topical therapies for Ps should not occur within 24 hours of a study visit so as not to interfere with clinical assessments for Ps.

All subjects in the study will be taking oral MTX (between 10 mg and 25 mg per week) and should also take a dietary supplement of oral folic acid every day, except on the day the subject is taking MTX over the study period.

For subjects who require isoniazid (INH) for TB prophylaxis, consideration should be given to administer pyridoxine (Vitamin B6) to prevent peripheral neuropathy.

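### Exclusion criterion 11 limits alcohol in grams, but its drink-to-gram conversion is inconsistent and, at ordinary strengths, understates wine and spirits

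*Protocol*

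**What the plan says.** Protocol Section 5.2.2, criterion 11, excludes a subject who "cannot maintain an alcohol intake of 30 g a day or less throughout the study". It then defines the unit for three beverages:

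- wine: "One standard drink is defined as 180 mL/6 oz (approx. 10 g) of wine"
- beer: "360 mL/12 oz (approx. 15 g) of regular beer"
- spirits: "45 mL/1.5 oz (approx. 10 g) of spirits"

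The synopsis (Section 1.2, Main Exclusion 11) carries the same figures: "one standard drink is defined as 180 mL/6 oz (approx. 10 g) of wine, 360 mL/12 oz (approx. 15 g) of regular beer", and the same spirits entry. Neither document states an alcoholic strength or gives any other conversion.

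On context, Protocol Section 5.2.3.2 says "All subjects in the study will be taking oral MTX (between 10 mg and 25 mg per week"). Table 1 schedules alcohol and nicotine use at Screening only. SAP Section 7.1 summarises alcohol use as current, former, never or unknown.

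**The concern.** The limit is in grams, but subjects usually describe intake in drinks, so the conversion is the natural link between the two. It has two problems.

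1. It does not define one quantity: a standard drink is about 10 g as wine or spirits and about 15 g as beer.
2. The wine and spirits grams look too small for their volumes, while the beer figure looks about right.

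If the conversion is used to judge the limit, the sponsor's threshold is not applied as stated, and a wine or spirits drinker is held to a looser standard than a beer drinker. This matters because every subject receives methotrexate and the same list excludes liver disease (criterion 4) and AST or ALT above twice the upper limit of normal (criterion 12). Entering a subject who fails the criteria is also a reportable deviation under Protocol Section 7.0, so the conversion can affect which deviations are recognised. The planned summaries hold no grams or volumes, so they would not show the problem.

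**Working it through.** **Inputs from the Protocol (criterion 11).** Limit 30 g/day; wine 180 mL = 10 g; beer 360 mL = 15 g; spirits 45 mL = 10 g.

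**Assumptions, not in the documents.** Ethanol density 0.789 g/mL; wine 12% ABV (range 10–14%); spirits 40% (35–45%); beer 5% (4–6%).

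**Step 1: relative strength, with no outside figure.** The stated grams per mL are 10/180 = 0.0556 for wine, 15/360 = 0.0417 for beer and 10/45 = 0.2222 for spirits. On these figures wine is 0.0556/0.0417 = 1.33 times as strong as beer, and spirits are 0.2222/0.0417 = 5.33 times as strong. The assumed central strengths give 12/5 = 2.4 and 40/5 = 8.

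**Step 2: strength implied by each pair.** ABV = grams / (mL × 0.789).

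- Wine: 10 / (180 × 0.789) = 7.0%
- Beer: 15 / (360 × 0.789) = 5.3%
- Spirits: 10 / (45 × 0.789) = 28.2%

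The stated grams are therefore too low for any wine above 7.0% and any spirit above 28.2%. This direction does not depend on the exact strength chosen within the assumed ranges.

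**Step 3: grams per stated serving.** Grams = mL × ABV × 0.789.

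- Wine: 180 × 0.12 × 0.789 = 17.0 g (14.2 at 10%, 19.9 at 14%), against 10 g stated
- Spirits: 45 × 0.40 × 0.789 = 14.2 g (12.4 at 35%, 16.0 at 45%), against 10 g stated
- Beer: 360 × 0.05 × 0.789 = 14.2 g (11.4 at 4%, 17.0 at 6%), against 15 g stated

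The beer figure is reproduced to within about 5%. The wine and spirits figures are not reproduced anywhere in their assumed ranges.

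**Step 4: intake that the conversion would count as 30 g/day.** Servings = 30 / stated grams. Intake = servings × grams from Step 3.

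| Beverage | Servings counted as 30 g | Intake at central strength | Range | Central value relative to 30 g |
|---|---|---|---|---|
| Wine | 30/10 = 3 | 51.1 g | 42.6–59.6 g | 51.1/30 = 1.70 |
| Spirits | 30/10 = 3 | 42.6 g | 37.3–47.9 g | 42.6/30 = 1.42 |
| Beer | 30/15 = 2 | 28.4 g | 22.7–34.1 g | 28.4/30 = 0.95 |

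The lowest value for wine or spirits, 37.3 g, is still 37.3/30 = 1.24 times the limit.

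**The case against.** The limit is stated in grams, the equivalents are marked approximate, and nothing in either document says that sites count drinks and convert them this way. Protocol Section 5.3.1.1 asks only for a history of alcohol use. A site that works out grams from volume and strength is unaffected. A reader might infer that subjects over the limit will be enrolled as a matter of course. The documents do not support that, because they describe no conversion procedure. The excess intake is conditional on a site using the only conversion that the protocol gives.

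A reader might also take 43 to 51 g/day as the range of intake. Those are two central values, one for spirits and one for wine. The range under the stated assumptions is 37 to 60 g, and all of it rests on strengths that the documents do not give. Nor is the issue confined to the start of methotrexate, since the criterion runs throughout the study.

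Other provisions limit the effect. Criterion 11 separately excludes clinically significant alcohol use in the last year. Criteria 1, 4, 12 and 13 cover contraindications to methotrexate, liver disease, abnormal liver tests and the investigator's general discretion. Chemistry is repeated at Weeks 8, 16 and 24. Section 5.4.1 provides for withdrawal on clinically significant laboratory results, and SAP Section 11.3.2.3 summarises liver tests by category.

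All of this stands, and it limits the consequence. It does not correct the figures: approximate does not cover central errors of 42% and 70% in the same direction for two of three beverages, and the two gram values for one standard drink need no outside assumption to be seen.

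**Conclusion.** The conversion in criterion 11 is inconsistent as written. One standard drink has two gram values. Given ethanol's density, the wine and spirits pairs require 7.0% and 28.2% ABV. At the assumed strengths the servings hold about 17 g (14–20) of alcohol as wine and 14 g (12–16) as spirits, against 10 g stated. If a site applies the conversion to reported drinks, an intake counted as 30 g/day is about 51 g (43–60) in wine or 43 g (37–48) in spirits, while two 5% beers hold about 28 g. The threshold would then vary by beverage.

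No endpoint, confidence interval or sample-size figure depends on this. It is also tempting to conclude that the 30 g limit is right and the gram equivalents are wrong. The text does not settle that: it would equally fit a sponsor who had a number of glasses in mind and gave poor gram figures. What the documents support is that limit, volumes and grams do not agree, not which of them should move or what the alcohol limit should be.

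**What to change.** The sponsor should reconcile the volumes, the gram equivalents and the 30 g/day limit in Protocol Section 5.2.2, criterion 11, and in the matching synopsis item. Each beverage line should state the assumed ABV, so that volume × ABV × 0.789 gives the stated grams. If the term standard drink is kept, it should mean one amount of alcohol; otherwise the three equivalents can be listed without it. Which figure changes is the sponsor's decision.

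The cost is a short wording amendment in two places, with the IEC/IRB approval described in Protocol Section 9.1. Depending on how the figures are reconciled, a few more wine or spirits drinkers may be found to be over the limit. No statistical analysis changes.
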